3.5 Rationale for Current Study

3.5.1 Rationale for Selection of Dose

The loading and maintenance dose level of LX9211 selected for evaluation in the current study was chosen based upon the safety, tolerability, and PK data observed from the prior single-dose and multiple-dose Phase 1 studies.

The doses studied in the SAD and MAD studies, in healthy volunteers, ranged from 5 to 300 mg. Single-dose administration demonstrated linear PK up to the highest tested dose (300 mg). There were no deaths, SAEs, discontinuations due to an AE, AEs of severe intensity, or any clinically significant laboratory, vital sign, physical exam (PE), or electrocardiogram (ECG) findings.

Multiple-dose administration demonstrated linear PK up to the highest tested dose (200 mg). There were no deaths, SAEs, discontinuations due to an AE, AEs of severe intensity, or any clinically significant laboratory, vital sign, PE, or ECG findings.

Based on the observed safety and tolerability data from single doses up to 300 mg and multiple doses up to 200 mg for 14 days, the dose level selected in this study, 200 mg loading dose

followed by 20 mg maintenance doses, respectively, are expected to be well tolerated and represent an adequate range for dose exploration.

3.6 Rationale for Study Design and Control Groups

The randomized, placebo-controlled, double-blind clinical design allows for unbiased comparison of efficacy and safety between LX9211 and placebo. The treatment duration (6 weeks) selected for this study was chosen based on the expectation of seeing an efficacy signal for the LX9211 200 mg treatment, which was based on human safety and tolerability.

Use of a concurrent placebo control, randomization, and double-blind administration of study drug are intended to minimize bias. Implementation of an unblinded interim analysis will allow for a reestimated increase in the sample size if indicated by the interim results. The study is designed as a group sequential trial to accommodate the interim analysis, and to improve upon such a design, the interim analysis effect size result is used not only to possibly increase the sample size, but to aid in decisions of early stopping for futility. The option of sample size reestimation (SSR) allows the study to power for a more optimistic effect, thereby minimizing up-front costs, while assuring a good probability of detecting a smaller important effect size by increasing the sample size if required.

4. Study Objectives

4.1 Primary Objective

To evaluate the efficacy of LX9211 in reducing pain related to postherpetic neuralgia (PHN)

4.2 Secondary Objective

To assess other effects and patient reported outcomes of LX9211 versus placebo during and following the Week 6 double-blind Treatment Period

4.3 Other Objectives

- Change from Baseline to Week 6 in the Neuropathic Pain Symptom Inventory (NPSI)
- Change from Baseline to each week in ADPS, based on Question 5 of the ZBPI
- Proportion of patients with $\geq 30\%$ reduction from Baseline in ADPS, based on Question 5 of the ZBPI by week
- Proportion of patients with $\geq 50\%$ reduction from Baseline in ADPS, based on Question 5 of the ZBPI by week

- Cumulative distribution function of percent change in ADPS based on Question 5 of the ZBPI from Baseline to Week 6 comparing the LX9211 treatment group to placebo
- Cumulative distribution function of percent change in ADPS based on Question 5 of the ZBPI from Week 6 to Week 11 comparing the LX9211 treatment group to placebo

5. Investigational Plan

5.1 Overall Study Design

This is a Phase 2, multicenter, randomized, double-blind, placebo-controlled, parallel-group study in patients with PHN.

[figure not shown]
Scheduled study visits in the clinic will occur during Screening; at the initiation of the 2-week single-blind placebo Run-in Period; on Day 1 (Baseline), and during Weeks 2, 4, and 6 of the double-blind Treatment Period, and Week 11 of the single-blind Safety Follow-up Period.

Male and female patients, ≥ 18 years of age, inclusive, with prior herpes zoster skin rash and PHN pain persisting for ≥ 3 months after healing of the herpes zoster skin rash, and who meet all inclusion and no exclusion criteria are eligible for enrollment.

Eligible patients may continue use 1 medication prescribed for PHN including pregabalin, gabapentin, and tricyclic antidepressant (TCA) medications, as long as they have been at stable doses for ≥ 1 month prior to Screening and are willing to maintain their doses for the duration of the study. Patients taking more than 1 permitted concomitant medication for the treatment of PHN and unable to washout all but 1 of these treatments for the duration of the study are not eligible. Use of any new medications, prescribed or over-the-counter (OTC), for treatment of PHN pain is not permitted during the course of the study. Use of any opioid medications for the management of PHN within the 2 months prior to Screening is not permitted.

The treatment schema is summarized in [Figure 5.1-1](#).

Figure 5.1–1 Treatment Schema

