6.6 Method of Assigning Patients to Treatment

Patients will be randomly assigned between 2 parallel treatment groups in a 1:1 manner. A randomization Schedule will be centralized and stratified by moderate or severe pain as derived from the ADPS collected during the Run-in period. The desired balances will be accomplished by use of randomly permuted blocks of fixed size. An Interactive Voice/Web Response System (IXRS) will be used as a central mechanism to assign patients to study treatment.

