10.1 Determination of Sample Size

Proposed Sample Size

The proposed sample size is derived by satisfying the original design assumptions made for the primary efficacy endpoint. It is assumed that the difference in treatment group means is 0 under the null hypothesis (H_0) and is unequal to 0 under the alternative hypothesis (H_1); a 2-sided hypothesis under test. Under the H_1 , the difference in group means of LX9211 minus placebo is expected to be -0.8 units with a common standard deviation of 1.0 units. These assumptions yield an effect size of 0.8. The effect size is the absolute value of the difference in treatment group means divided by the common standard deviation of that difference. A uniform dropout rate of 0.15 is anticipated, and adjustment of the effect size for this rate results in an estimate 0.68; the adjusted difference in group means is equal to -0.8 units \times 0.85 = -0.68. For a 2-sided test sized at $\alpha = 0.05$, 37 patients per treatment group are required under a 1:1 randomization ratio to detect the stated treatment difference under H_1 with statistical power equal to 82.27% under a single stage design. The total planned $N = 74$ patients.

This study is designed as a group sequential trial with 1 interim look at approximately the 50% information time and a final analysis at 100%. A non-binding futility boundary will be used to test for futility of the primary endpoint. The futility boundary is 1-sided with $\alpha = 0.025$ and for the parameters specified, a power estimate of 82.53% is derived.

Sample Size Reestimation

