7.1 General Principles

All data processing, summarization and analyses will be performed using Hosted SAS Environment / Version 9.4 (or later) of the SAS® (SAS Institute, Cary, NC) statistical software package.

The following principles will be applied to all tables, figures, and listings (TFLs) unless otherwise stated:

Principle	Value
Significant tests	2-sided and use a 5% significance level for the main effect of study treatment
Treatment group labels and order presented	LX9211 200 mg/20 mg Placebo Total (if applicable)
Tables	Data in summary tables presented by treatment group, assessment (where applicable) and visit (where applicable)
Listings	All data collected presented by treatment group, site, patient, and visit (where applicable), date, unless otherwise specified

Statistical Analysis Plan Final v3.0

Lexicon Pharmaceuticals, Inc.
Protocol ID: LX9211.1.202-PHN

Labcorp Study ID: [REDACTED]

Principle	Value
Descriptive summary statistics for continuous variables	Number of patients/observations with non-missing data (n), mean, standard deviation (SD), median, minimum and maximum. If n=0 then other statistics will be blank.
Descriptive summary statistics for categorical variables	Frequency counts and associated percentages [n (%)] presented to 1 decimal place.
Denominator for percentages	Number of patients per treatment group in the analysis population, unless stated otherwise in table shell(s)
Include "Missing" as category	Yes, when the number missing is greater than 0 for at least 1 treatment group
Display for 0 percentages	Leave Blank
Display for treatment compliance and percentage change from Baseline	Present Mean and Median to 1 decimal place and SD to 2 decimal places
Display to 1 more decimal place than collected value	Mean Mean Difference Median Confidence Interval
Display to 2 more decimal places than collected value	SD Standard Error
Display for p-values	x.xx for p-value >0.05 x.xxx for p-value ≤ 0.05 and ≥0.001 <0.001 for p-value <0.001
Limit of precision for displays	3 decimal places
Date Format	DDMMYYYY
Display for analysis not done	NC (not calculated), NA (not applicable), ND (not done), or NR (not reported). Refer to table shells.

For continuous efficacy variables that are derived as percentage change from Baseline outcomes, the applied analyses and their results will be used for descriptive purposes.

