7.4 Demographics and Other Baseline Characteristics

Demographic and Baseline characteristics will be listed and summarized by treatment group and overall for the mITT population. Standard descriptive statistics will be presented for the continuous variables of:

- Age at time of Informed Consent (years)
- Weight (kg), to convert pounds (lbs) to kilograms, multiply the pound value by 0.45359237
- Height (cm), to convert inches (in) to centimeters, multiply the inches value by 2.54
- Body mass index (BMI) (kg/m^2)
- Sitting systolic blood pressure (BP) (mm Hg)
- Sitting diastolic BP (mm Hg)
- Pulse rate (beats per minute [bpm])
- Respiration rate (breaths/min)
- Temperature (C), to convert Fahrenheit (F) to Celsius, (Fahrenheit value (F) – 32) * 5/9
- HADS-Depression and HADS-Anxiety subscores

The total counts and percentages of patients will be presented for the categorical variables of:

- Age at time of Informed Consent (grouped as <75 years, ≥75 years)
- Sex
- Race
- Ethnicity
- Fertility status (females only)
- Method of contraception
- Baseline pain severity categorized by randomization strata (as derived using average pain scores collected during the 14-day Run-in data)
- Baseline ADPS (as derived using week 2 of Run-in data)
- Baseline postherpetic neuralgia (PHN) drug use (Yes, No)

A summary of Baseline physical examination data will be presented by treatment group and overall for the mITT population.

Other Baseline measurements, such as laboratory evaluations and ECG, will be summarized by treatment group with the post-Baseline measurements.

No formal tests of statistical significance will be performed on the demographic and Baseline characteristics data.

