7.6.1 Primary Efficacy Analysis

The primary endpoint is the change from Baseline to Week 6 in ADPS, based on Question 5 of the ZBPI, the 11-point numerical rating scale (0 [No Pain] to 10 [Pain as bad as you can imagine]). The primary analysis will be based on observed data including data measured after the initiation of rescue medications.

Baseline is defined as the average of the Week 2 Run-in Period data collected by patients in the daily pain diary, provided that ≥ 5 days from that period are available for analysis. The post-Baseline values will be calculated by week as the mean value of the Question 5 for ADPS of the ZBPI, rated by patients each evening and collected during the target week period. A minimum of 4 non-missing data within the target week period is required for the calculation. The change from

Baseline values at post-Baseline weeks will be calculated as the absolute difference between the Baseline value and post-Baseline values, i.e.

$$\text{change from Baseline} = \text{post-Baseline value} - \text{Baseline value}$$

The ADPS calculated for each post-Baseline week until Week 6, and the change from Baseline in ADPS at post-Baseline weeks until Week 6 will be summarized by Week using standard descriptive statistics. Data from all study visits, scheduled and unscheduled, and from the daily pain diary will be listed.

A restricted maximum likelihood-based, MMRM approach will be used to assess the difference between LX9211 and placebo in the primary endpoint (ie, change from Baseline to Week 6 in the ADPS derived from data collected daily from Question 5 of the ZBPI instrument). The MMRM model will include fixed effects of treatment, week, treatment-by-week interaction, the randomization stratum of Baseline pain severity (moderate, severe), and the Baseline ADPS score as a covariate. An unstructured covariance structure will be used to model the within-patient error. The Kenward-Roger approximation will be used to estimate the denominator degrees of freedom. Other covariance structures will be explored should convergence not be met.

The adjusted mean change in ADPS from Baseline to Week 6 for each treatment group and the 95% confidence intervals (CIs) will be estimated in the framework of this model, as well as the between-group differences (comparing LX9211 to placebo) and the 95% CIs for the difference.

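### Background PHN drug use is already collected but is missing from the primary model: no bias on average, but a near-free covariate is left out

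*Protocol*

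**What the plan says.** **Population.** Protocol 5.1 states: "Eligible patients may continue use 1 medication prescribed for PHN including pregabalin, gabapentin, and tricyclic antidepressant (TCA) medications". The dose must have been stable for at least a month before Screening and must be maintained. A background drug is allowed but not required, so LX9211 is add-on therapy in some patients and the only PHN drug in others.

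**Randomization.** Protocol 6.6 describes a schedule "stratified by moderate or severe pain as derived from the ADPS collected during the Run-in period". No other factor is named.

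**Primary model.** SAP 7.6.1 specifies an MMRM with "fixed effects of treatment, week, treatment-by-week interaction, the randomization stratum of Baseline pain severity (moderate, severe), and the Baseline ADPS score as a covariate". Protocol 10.4.2.1 lists the same terms. The ANCOVA after multiple imputation (SAP 7.6.3) has treatment, severity stratum and Baseline score. None of these models has a background-drug term.

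**Where the factor does appear.** SAP 7.4 lists "Baseline postherpetic neuralgia (PHN) drug use (Yes, No" among the categorical Baseline characteristics. SAP 7.6.4 makes it a subgroup factor for the primary endpoint, using the primary model's covariates, and labels all subgroup analyses exploratory. Protocol 10.4.4 names only pain severity and sex, and leaves further subgroups to the SAP.

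**The concern.** Drug use at entry is fixed before randomization and recorded for everyone, and the sponsor thought it relevant enough to examine as a subgroup. If users and non-users with the same Baseline pain score change by different amounts over six weeks, leaving the factor out has two linked effects. The difference stays in the error variance, and an uneven split between arms moves this one trial's estimate. With 37 per arm and no stratification on the factor, sizeable splits are not rare.

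The interim look is more exposed. It uses 38 patients, and the observed mean difference and standard deviation feed the sample size re-estimation (SAP 2.3) as well as the futility assessment (SAP 7.8).

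The subgroup analysis shows the effect within users and within non-users. No planned analysis adjusts the overall Week 6 estimate for the factor.

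**Working it through.** **Inputs from the documents**
- Test: "2-sided and use a 5% significance level for the main effect of study treatment" (SAP 7.1).
- Sample size: "37 patients per treatment group are required under a 1:1 randomization ratio" (Protocol 10.1).
- Effect: "expected to be -0.8 units with a common standard deviation of 1.0 units" (Protocol 10.1), multiplied by 0.85 for 15% dropout to give 0.68.
- Power: "statistical power equal to 82.27% under a single stage design" (Protocol 10.1).

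**Step 1: reproduce the stated power.** A two-sample t-test with 37 per arm, difference 0.68, SD 1.0 and 72 degrees of freedom (noncentral t) gives 82.27%, an exact match.

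**Inputs that must be assumed**
- *p*: share of patients on a background drug. The main case is 0.5.
- *d*: difference between users and non-users in Week 6 change at equal Baseline score. The range is 0.3 to 0.5 points, with 0 as the null case.
- The planning SD of 1.0 is taken as the SD left after the model's existing terms.
- A single comparison at Week 6 stands in for the MMRM.

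**Step 2: chance imbalance.** The SD of the between-arm difference in user share is √(2p(1−p)/37).
- p = 0.5: √(0.5/37) = 0.116, and 1.96 × 0.116 = 0.228, about 23 percentage points.
- p = 0.3 or 0.7: √(0.42/37) = 0.107, and 1.96 × 0.107 = 0.209, about 21 points.
- Exact binomial at p = 0.5: a gap of at least 10 points has probability 42%, and of at least 20 points 8%.
- Interim, 19 per arm, p = 0.5: √(0.5/19) = 0.162, about 16 points.

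**Step 3: shift in the unadjusted estimate at the 95% limit, and gain from adjustment.** Shift = 0.228 × d. Residual variance = 1 − p(1−p)d². Power is recomputed at 0.68 and 37 per arm with 71 degrees of freedom. Results for p = 0.5:

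| d (points) | Shift (points) | Shift / 0.68 | Residual variance | Power, adjusted |
|---|---|---|---|---|
| 0 | 0 | 0% | 1.000 | 82.25% |
| 0.3 | 0.07 | 10% | 0.978 | 83.1% |
| 0.5 | 0.11 | 17% | 0.938 | 84.6% |

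At d = 0.5 and p = 0.3 the adjusted power is 84.2%, so the result depends little on the user share in this range. The shift and the variance reduction are two views of one quantity and should not be added together.

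**Step 4: the definition.** SAP 7.6.4 defines users as patients who took concomitant PHN medications and gives a list. SAP 7.4.2 counts as concomitant any drug started on or after the first double-blind dose, so the factor as worded can pick up post-randomization use. The drug lists also differ. SAP 7.6.4 includes duloxetine, venlafaxine, desvenlafaxine and valproic acid, which Protocol 5.1 does not name. Amitriptyline is the only tricyclic in the SAP list, whereas Protocol 5.1 refers to tricyclics as a class.

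**The case against.** The strongest reply is that no error has been shown. The model contains the stratification factor and the Baseline score. Randomization balances everything else on average, and the standard error already allows for chance imbalance. Which further covariates to add is a design preference. This stands: there is no bias on average, unconditional type I error is held, and the stated power is correct. A reader might infer from the omission that the Week 6 estimate is biased or the trial underpowered, and the documents support neither.

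Baseline ADPS is measured in the second run-in week, on the stable drug, and is a covariate. Differences in pain level are therefore largely absorbed already. Only a difference in change at equal Baseline counts. This also stands.

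A reader might also infer that users are treatment-resistant and non-users are not. The documents do not say so. Exclusion criterion 8 lets in patients who stopped other neuropathic pain treatments at least a month before Screening, so non-users may have a similar history. Neither the direction nor the existence of a prognostic difference is established.

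Larger figures are possible only under strong assumptions. A residual difference of 0.8 points would give a shift of 0.18 and power of about 88%, but it would equal the whole planned drug effect.

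Finally, the Baseline table shows any imbalance, and the subgroup estimates are free of imbalance on this factor. That makes the issue visible but leaves the pooled estimate unadjusted.

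**Conclusion.** The point holds as a modest efficiency improvement, not as a flaw that threatens validity. The plan leaves out of its primary model a pre-randomization factor that it already collects and examines.

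With 50% users and a residual difference of 0.3 to 0.5 points (both assumed), adjustment gains about 0.8 to 2.3 power points. It also removes a possible shift of 0.07 to 0.11 points at the 95% limit of chance imbalance. If drug use does not predict change beyond Baseline score, there is essentially no gain, and power goes from 82.27% to 82.25%. The case for acting rests on that small cost, not on evidence that the factor is prognostic.

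The definition needs tidying in any case, because the subgroup factor as worded is not strictly a baseline variable.

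**What to change.** Before unblinding:

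1. **Define the factor once.** Baseline PHN drug use (yes/no) means a drug taken for PHN and ongoing at the first double-blind dose. Drugs started after that dose do not count. Reconcile the drugs named in Protocol 5.1 with the SAP 7.6.4 list, and use the same definition for the Baseline table, the covariate and the subgroup.
2. **Add it as a fixed effect** to the primary MMRM in SAP 7.6.1, with matching text in Protocol 10.4.2.1.
3. **Use the same term** in the supplementary MMRM that excludes data after rescue, in both the multiple-imputation model and its ANCOVA (SAP 7.6.3), and in the model used at the interim analysis. Adding it to the ANCOVA but not to the imputation model would leave the two mismatched.
4. **Omit the term** within the PHN drug use subgroups, as SAP 7.6.4 already does for pain severity.

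Adding the factor to the stratification is not needed. It would give 2 arms × 2 severity levels × 2 drug-use levels = 8 cells, averaging 74/8 ≈ 9 patients.

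The cost is one model degree of freedom and a SAP revision, with no new data or patients. Changing the protocol text also requires an amendment with IRB approval (Protocol 11.4).

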5.1.1 Screening Period

After signing the Informed Consent Form (ICF), all patients will enter a Screening Period of up to 2 weeks. Patients using non-opioid medications that are prohibited by the protocol must discontinue or washout of these medications as directed by the protocol prior to entering the Screening period. Following confirmation of eligibility criteria, patients will enter the following study periods:

5.1.2 Run-in Period

After meeting Screening eligibility criteria, patients will enter a 2-week single-blind Run-in Period. On Day 1 of the Run-in period, patients will be administered 4 tablets of single blind study drug at the site. For the remaining duration of the Run-in Period, patients will take a single tablet of study drug every morning. Each evening patients will rate and record intensity of their PHN pain based on Question 5 of the ZBPI by answering the question “Please rate your pain by indicating the one number that best describes your pain on the average in the last 24 hours”, on the 11-point numerical rating scale (0 [No Pain] to 10 [Pain as bad as you can imagine]). The ADPS will be calculated using all available daily pain diary data. The mean value of the ADPS derived over Week 2 will serve as the Baseline measure used for analyses. In order to qualify for randomization, patients must have completed $\geq 70\%$ of the daily pain diary entries during the second week of the Run-in Phase, meet criteria for moderate to severe pain and demonstrate $\geq 80\%$ compliance with taking the expected amount of placebo tablets during the Run-in Period. During the Run-in Period patients will not be allowed to use any rescue medication. On the morning of the Run-in Visit, patients may consume a light meal prior to the visit.

Note: Patients who fail Screening due to laboratory values may have those assessments repeated and be rescreened **once** after discussion with the Sponsor’s Medical Monitor.

